7.0 REGULATORY AND REPORTING REQUIREMENTS

The entities providing oversight of safety and compliance with the protocol require reporting as outlined below.

The Washington University Human Research Protection Office (HRPO) requires that all events meeting the definition of unanticipated problem or serious noncompliance be reported as outlined in Section 7.2.

The FDA requires that all serious and unexpected adverse events be reported as outlined in Section 7.4. In addition, any fatal or life-threatening adverse experiences where there is a reasonable possibility of relationship to study intervention must be reported.

Novartis requires that all serious adverse events be reported as outlined in Section 7.9.

7.1 Definitions

7.1.1 Adverse Events (AEs)

Definition: any unfavorable medical occurrence in a human subject including any abnormal sign, symptom, or disease.

Grading: the descriptions and grading scales found in the revised NCI Common Terminology Criteria for Adverse Events (CTCAE) version 4.0 will be utilized for all toxicity reporting. A copy of the CTCAE version 4.0 can be downloaded from the CTEP website.

Attribution (relatedness), Expectedness, and Seriousness: the definitions for the terms listed that should be used are those provided by the Department of Health and Human Services' Office for Human Research Protections (OHRP). A copy of this guidance can be found on OHRP's website:
<http://www.hhs.gov/ohrp/policy/advevntguid.html>

7.1.2 Serious Adverse Event (SAE)

Definition: any adverse drug experience occurring at any dose that results in any of the following outcomes:

- Death
- A life-threatening adverse drug experience
- Inpatient hospitalization or prolongation of existing hospitalization
- A persistent or significant disability/incapacity (i.e., a substantial disruption of a person's ability to conduct normal life functions)
- A congenital anomaly/birth defect
- Any other experience which, based upon appropriate medical judgment, may jeopardize the subject and may require medical or surgical intervention to prevent one of the outcomes listed above

All unexpected SAEs must be reported to the FDA.

7.1.3 Unexpected Adverse Experience

Definition: any adverse drug experience, the specificity or severity of which is not consistent with the current investigator brochure (or risk information, if an IB is not required or available).

Events that are both serious AND unexpected must be reported to the FDA.

7.1.4 Life-Threatening Adverse Experience

Definition: any adverse drug experience that places the subject (in the view of the investigator) at immediate risk of death from the reaction as it occurred, i.e., it does not include a reaction that, had it occurred in a more severe form, might have caused death.

Life-threatening adverse experiences must be reported to the FDA.

7.1.5 Unanticipated Problems

Definition:

- unexpected (in terms of nature, severity, or frequency) given (a) the research procedures that are described in the protocol-related documents, such as the IRB-approved research protocol and informed consent document; and (b) the characteristics of the subject population being studied;
- related or possibly related to participation in the research (“possibly related” means there is a reasonable possibility that the incident, experience, or outcome may have been caused by the procedures involved in the research); and
- suggests that the research places subjects or others at a greater risk of harm (including physical, psychological, economic, or social harm) than was previously known or recognized.

7.1.6 Noncompliance

Definition: failure to follow any applicable regulation or institutional policies that govern human subjects research or failure to follow the determinations of the IRB. Noncompliance may occur due to lack of knowledge or due to deliberate choice to ignore regulations, institutional policies, or determinations of the IRB.

7.1.7 Serious Noncompliance

Definition: noncompliance that materially increases risks, that results in substantial harm to subjects or others, or that materially compromises the rights or welfare of participants.

7.1.8 Protocol Exceptions

Definition: A planned deviation from the approved protocol that are under the research team's control. Exceptions apply only to a single participant or a singular situation.

Local IRB pre-approval of all protocol exceptions must be obtained prior to the event. For secondary sites, the Washington University PI will issue approval of the exception, but it must also be submitted to the local IRB with documentation of approval forwarded to Washington University. Washington University IRB approval is not required for protocol exceptions occurring at secondary sites.

7.2 Reporting to the Human Research Protection Office (HRPO) at Washington University

The PI is required to promptly notify the IRB of the following events:

- Any unanticipated problems involving risks to participants or others which occur at WU, any BJH or SLCH institution, or that impacts participants or the conduct of the study.
- Noncompliance with federal regulations or the requirements or determinations of the IRB.
- Receipt of new information that may impact the willingness of participants to participate or continue participation in the research study.

These events must be reported to the IRB within **10 working days** of the occurrence of the event or notification to the PI of the event. The death of a research participant that qualifies as a reportable event should be reported within **1 working day** of the occurrence of the event or notification to the PI of the event.

7.3 Reporting to the Quality Assurance and Safety Monitoring Committee (QASMC) at Washington University

The PI is required to notify the QASMC of any unanticipated problem occurring at WU or any BJH or SLCH institution that has been reported to and acknowledged by HRPO as reportable. (Unanticipated problems reported to HRPO and withdrawn during the review process need not be reported to QASMC.)

QASMC must be notified within **10 days** of receipt of IRB acknowledgment via email to a QASMC auditor.

7.4 Reporting Requirements for Secondary Sites

The research team at each secondary site is required to promptly notify the Washington University PI and research coordinator of all reportable events (as described in Section 7.6) within **1 working day** of the occurrence of the event or notification of the secondary site's PI of the event. This notification may take place via email if there is not yet enough information for a formal written report (using either an FDA MedWatch form if required or an institutional SAE reporting form if not). A formal written report must be sent to the Washington University PI and research coordinator within **10 working days** of the occurrence of the event or notification of the secondary site's PI of the event. The death of a research participant that qualifies as a reportable event should be reported within **1 working day** of the occurrence of the event or notification of the secondary site's PI of the event.

The research team at a secondary site is responsible for following its site's guidelines for reporting applicable events to its site's IRB according to its own institutional guidelines. The research team at Washington University is responsible for reporting all applicable events to the FDA.

7.5 Reporting to Secondary Sites

The Washington University PI (or designee) will notify the research team at each secondary site of all reportable events that have occurred at other sites within **10 working days** of the occurrence of the event or notification of the PI of the event. This includes events that take place both at Washington University and at other secondary sites, if applicable.

7.6 Reporting to Novartis

A serious adverse event (SAE) is an undesirable sign, symptom or medical condition which:

- is fatal or life-threatening
- results in persistent or significant disability/incapacity
- constitutes a congenital anomaly/birth defect
- requires inpatient hospitalization or prolongation of existing hospitalization, unless hospitalization is for:
 - routine treatment or monitoring of the studied indication, not associated with any deterioration in condition (specify what this includes)
 - elective or pre-planned treatment for a pre-existing condition that is unrelated to the indication under study and has not worsened since the start of study drug
 - treatment on an emergency outpatient basis for an event not fulfilling any of the definitions of a SAE given above and not resulting in hospital admission
 - social reasons and respite care in the absence of any deterioration in the patient's general condition

- is medically significant, i.e., defined as an event that jeopardizes the patient or may require medical or surgical intervention to prevent one of the outcomes listed above

The principal investigator has the obligation to report all serious adverse events to the IRB and Novartis Pharmaceuticals Drug Safety and Epidemiology Department (DS&E) (For patients taking Pazopanib / Novartis drugs).

To ensure patient safety, every SAE, regardless of suspected causality, occurring

- after the patient has provided informed consent and until at least 30 days after the patient has stopped study treatment/participation
- after protocol-specified procedures begin (e.g., placebo run-in, washout period, double-blind treatment, etc.) and 30 days after the patient has stopped study treatment
- after the start of any period in which the study protocol interferes with the standard medical treatment given to a patient (e.g., treatment withdrawal during washout period, change in treatment to a fixed dose of concomitant medication) and until 30 days after the patient has stopped study treatment

All Events must be reported to Novartis within 24 hours of learning of its occurrence. Information about all SAEs is collected and recorded on a Serious Adverse Event Report Form; all applicable sections of the form must be completed in order to provide a clinically thorough report. The investigator must assess and record the relationship of each SAE to each specific study treatment (if there is more than one study treatment), complete the SAE Report Form in English, and send the completed, signed form by fax to **([contact])** within 24 hours to the oncology Novartis DS&E department with the provided FAX cover sheets.

This includes serious, related, labeled (expected) and serious, related, unlabeled (unexpected) adverse experiences. All deaths during treatment or within 30 days following completion of active protocol therapy must be reported within 5 working days.

Any SAEs experienced after this 30 day period should only be reported to Novartis if the investigator suspects a causal relationship to the study drug. Recurrent episodes, complications, or progression of the initial SAE must be reported as follow-up to the original episode within 24 hours of the investigator receiving the follow-up information. A SAE occurring at a different time interval or otherwise considered completely unrelated to a previously reported one should be reported separately as a new event. The end date of the first event must be provided.

The original copy of the SAE Report and the fax confirmation sheet must be kept within the Trial Master File at the study site.

Follow-up information is sent to the same fax number as the original SAE Report Form was sent, using a new fax cover sheet, stating that this is a follow-up to the previously reported SAE, and giving the date of the original report. Each re-occurrence, complication, or progression of the original event should be reported as a follow-up to that event regardless of when it occurs. The follow-up information should describe whether the event has resolved or continues, if and how it was treated, whether the blind was broken or not (if applicable), and whether the patient continued or withdrew from study participation.

If the SAE is not previously documented in the Pazopanib Investigator Brochure or Package Insert (new occurrence) and is thought to be related to the Novartis study drug, a DS&E associate may urgently require further information from the investigator for Health Authority reporting. Novartis may need to issue an Investigator Notification (IN), to inform all investigators involved in any study with the same drug that this SAE has been reported. Suspected Unexpected Serious Adverse Reactions (SUSARs) will be collected and reported to the competent authorities and relevant ethics committees in accordance with Directive 2001/20/EC or as per national regulatory requirements in participating countries.

To ensure patient safety, each pregnancy occurring while the patient is on study treatment must be reported to Novartis within 24 hours of learning of its occurrence.

7.7 Timeframe for Reporting Required Events

Reportable adverse events will be tracked for 30 days following the last day of study treatment.

8.0 PHARMACEUTICAL INFORMATION

8.1 Pazopanib

8.1.1 Pazopanib Description

GW786034 (pazopanib) is a vascular endothelial growth factor (VEGF) receptor tyrosine kinase inhibitor (TKI) manufactured by Novartis for oncology indications (as an oral formulation) and for ophthalmology indications (eye drops and low dose oral). Pazopanib has been approved by the U.S. Food and Drug Administration (FDA) for the treatment of patients with advanced renal cell carcinoma (RCC) (New Drug Application [NDA] #022465).

Chemical Name: 5-[[4-[(2,3-Dimethyl-2H-indazol-6-yl)methylamino]-2-pyrimidinyl]amino]-2-methylbenzenesulfonamide monohydrochloride

Molecular Formula: C₂₁H₂₃N₇O₂S • HCl

Molecular Weight: 473.99 g/mol (monohydrochloride salt); 437.53 g/mol (free base)

8.1.2 Pharmacokinetics and Drug Metabolism

Pazopanib is absorbed orally with median time to achieve peak concentrations of 2 to 4 hours after the dose. Daily dosing at 800 mg results in geometric mean AUC and C_{max} of 1,037 mcg·hr/mL and 58.1 mcg/mL (equivalent to 132 µM), respectively.

8.1.3 Supplier(s)

Pazopanib will be provided to the sites by Novartis Pharmaceuticals Corporation using a separate drug supply request form.

8.1.4 Dosage Form and Preparation

Pazopanib is supplied as 200 mg and/or 400 mg tablets. Tablets are packaged in a sealed bottle with an affixed content label identifying the product.

8.1.5 Storage and Stability

Store at room temperature between 20°C and 25°C; excursions permitted to 15°C to 30°C.

8.1.6 Administration

Pazopanib should be taken orally without food at least one hour before or two hours after a meal. Dosing will be as described in Section 5.1.

8.1.7 Safety Information

Information on safety, side effects and adverse events can be found in the most current Pazopanib Investigator Brochure.

9.0 CORRELATIVE STUDIES

9.1 Quality of Life

Quality of life will be measured using the FACT-G7 validated survey (Appendix D) at baseline, C1D15, and on Day 1 of each cycle.

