2.2 Secondary Objectives

1. To determine the rate of progression-free survival (PFS) in patients with soft tissue sarcoma not candidates for chemotherapy treated with first-line pazopanib.
2. To determine the rate of overall survival (OS) in patients with soft tissue sarcoma not candidates for chemotherapy treated with first-line pazopanib.
3. To evaluate the quality of life of patients with soft tissue sarcoma not candidates for chemotherapy treated with first-line pazopanib.
4. To correlate serum sVEGFR2 and PICG levels with outcomes.

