5.0 TREATMENT PLAN

5.1 Agent Administration

Pazopanib will be started at a dose of 200 mg BID for four days, then escalated to a dose of 400 mg BID for four days (if tolerated), then escalated once more to a dose of 800 mg QD for the duration of participation (if tolerated) or until dose reduction, if necessary. Pazopanib should be taken orally without food at least one hour before or two hours after a meal. One cycle of pazopanib is 28 days. The tablets should be swallowed whole and must not be crushed or broken. The time of day the tablets are taken should be relatively constant.

If a dose is missed, the subject should take the dose as soon as possible, but only if there are 12 or more hours remaining before the next dose is due. If the next dose is due in less than 12 hours, the subject should skip the missed dose and take the next dose as scheduled.

If vomiting occurs after taking pazopanib, the subject should not take a replacement dose for that dose, but should resume taking pazopanib at the next scheduled dose. If vomiting persists, the subject should be instructed to notify the investigator.

Please note that a Monday or Thursday start is recommended to avoid weekend blood draws for pharmacokinetic testing.

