5.4 Duration of Therapy

If at any time the constraints of this protocol are considered to be detrimental to the patient's health and/or the patient no longer wishes to continue protocol therapy, the protocol therapy should be discontinued and the reason(s) for discontinuation documented in the case report forms.

In the absence of treatment delays due to adverse events, treatment may continue indefinitely until one of the following criteria applies:

- Documented and confirmed disease progression
- Death
- Adverse event(s) that, in the judgment of the investigator, may cause severe or permanent harm or which rule out continuation of study drug
- General or specific changes in the patient's condition render the patient unacceptable for further treatment in the judgment of the investigator
- Suspected pregnancy
- Serious non-compliance with the study protocol
- Lost to follow-up
- Patient withdraws consent
- Investigator removes the patient from study
- The Siteman Cancer Center decides to close the study

Patients who prematurely discontinue treatment for any reason other than withdrawal of consent will be followed as indicated in the study calendar.

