10.0 STUDY CALENDAR

Screening assessments must be performed no more than 14 days prior to start of study treatment, except scans which may take place up to 28 days prior to the start of treatment. After the start of study treatment, there is a ± 7 day window for all exams, scans, labs and procedures to be performed. Please note, there is also a ± 7 day window for treatment and for routine office visits.

	Screening	D1 of each cycle	C1D5	C1D8	C1D9	C1D15 and C2D15	End of every even-numbered cycle	EOT	F/U ¹	
Informed consent	X									
PE, H&P, PS	X	X						X		
VS	X	X		X				X		
CBC	X	X		X				X		
CMP	X	X		X				X		
LFTs ²	X	X ²		X ²		X ²		X		
Pregnancy test ³	X							X		
UPC	X	X ⁴						X		
TSH, FT4	X	X ⁵								
PT/PTT, INR	X							X		
ECG	X	X ⁶								
ECHO ¹⁰	X									
CT scan	X						X	X		
Pazopanib		X	-----					X ⁷		
FACT-G		X ⁸				X ⁸				
Blood for biomarkers		X ⁹								
Collect/review drug diary		X								
Toxicity assessment	X	X						X		

1. Every 3 months until death.

2. Monitor serum liver tests (total bilirubin, ALT/AST) before initiation of treatment with pazopanib and on C1D15, C2D1, C2D15, C3D1, C4D1, C5D1, and as clinically indicated (± 3 days). Periodic monitoring should continue after C5.

3. Women of childbearing potential only.

4. D1 of each cycle through C6, then D1 of every even-numbered cycle thereafter.

5. Monitor between every 8 to every 16 weeks.

6. C2D1, C4D1, C7D1, and then every 16 weeks (D1 of every 4th cycle) until EOT.

7. To be taken PO each day. Each cycle is 4 weeks long. See Section 5.1 for dosing instructions.

8. Baseline (prior to C1D1), C1D15, and D1 of every cycle thereafter.

9. Baseline (prior to C1D1), C2D1, C3D1, and C4D1.

10. Baseline (prior to C1D1) and periodic reassessment as needed and/or as indicated. Consistent diagnostic imaging should be used throughout study.

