11.0 DATA SUBMISSION SCHEDULE

Case report forms with appropriate source documentation will be completed according to the schedule listed in this section.

Case Report Form	Submission Schedule
Original Consent Form	Prior to registration
Registration Form Eligibility Form On-Study Form	Prior to starting treatment
Treatment Form Pill Diary	Every cycle
QOL Form	Baseline C1D15 Day 1 of every cycle thereafter
Correlatives Form	Baseline C1D5 C1D9 C2D1 C3D1 C4D1
Toxicity Form	Continuous
Treatment Summary Form	Completion of treatment
Follow Up Form	Every 3 months until death
Tumor Measurement Form	Baseline, end of every even numbered cycle, and end of treatment
MedWatch Form	See Section 7.0 for reporting requirements

Any queries generated by Washington University must be responded to within 28 days of receipt by the participating site. The Washington University research team will conduct a regular review of data status at all secondary sites, with appropriate corrective action to be requested as needed.

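### FACT-G7 is not collected at the end-of-treatment visit, so post-baseline quality of life comes only from patients still on pazopanib, a group more selected with each cycle

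*Combined protocol and SAP*

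**What the plan says.** Quality of life is the third secondary objective: "To evaluate the quality of life of patients with soft tissue sarcoma not candidates for chemotherapy treated with first-line pazopanib" (section 2.2). The target is the treated population, with no restriction to patients who remain on drug.

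Three places give the collection schedule, and they agree on the point at issue:

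- Section 9.1: "at baseline, C1D15, and on Day 1 of each cycle".
- Section 10.0, footnote 8: "Baseline (prior to C1D1), C1D15, and D1 of every cycle thereafter". The FACT-G row of the calendar is marked under Day 1 of each cycle and under the column shared by C1D15 and C2D15. Its EOT and follow-up cells are empty.
- Section 11.0, QOL Form row: "Baseline C1D15 Day 1 of every cycle thereafter".

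The EOT column of the same calendar already carries physical exam and performance status, vital signs, laboratory tests, CT and toxicity assessment. In section 11.0 the Tumor Measurement Form is due at end of treatment; the QOL Form is not.

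Section 15.2 covers the clinical benefit rate, the two biomarkers, PFS and OS. It gives no quality-of-life summary, model or rule for missing forms.

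**The concern.** Collection of the outcome stops for reasons tied to the outcome. A patient who progresses, cannot tolerate the drug or declines leaves treatment, and from then on no form is due. What remains at each later cycle is a group selected for doing well enough to continue. A summary by cycle in that group will tend to look better than the experience of everyone who was treated.

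This matters more than usual here. The rationale in section 1.3 is that frail patients unfit for doxorubicin may tolerate pazopanib well, and quality of life bears directly on that premise. A value not collected at discontinuation cannot be recovered by analysis afterwards.

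**Working it through.** **1. Does collection stop with treatment?**

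- Section 5.1: "One cycle of pazopanib is 28 days". Day 1 visits are therefore treatment visits.
- Section 5.4 ends treatment for "Documented and confirmed disease progression", death, adverse events, a change in the patient's condition, and several administrative reasons.
- Section 5.4 also says: "Patients who prematurely discontinue treatment for any reason other than withdrawal of consent will be followed as indicated in the study calendar". The calendar has no FACT-G entry at EOT or in follow-up.
- Section 5.5 allows the three-monthly follow-up to be met by a phone call or a death-index check for survival.

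Together these mean that no FACT-G7 is due once pazopanib has stopped.

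**2. The plan's own figures.** The plan states no quality-of-life figure. The only design rates available are those in section 15.1: 56 patients, 16-week clinical benefit of 20% (unfavourable) against 35% (desired), cut-off 17. An exact binomial calculation gives a one-sided alpha of 4.32%, as stated, and power of 80.64% against the stated 81.64%. That one-point difference has no bearing on this point; the rates are used below only to size attrition.

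**3. Patients contributing at C5D1.** C5D1 falls 4 × 4 = 16 weeks after the start. Assumption: a patient without clinical benefit at week 16 is off drug.

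- At 20%: 56 × 0.20 = 11.2, so about 11 contribute and 45 do not.
- At 35%: 56 × 0.35 = 19.6, so about 20 contribute and 36 do not.

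**4. Sensitivity.** Section 1.2 cites a median PFS of 4.6 months on pazopanib in previously treated patients. Assume exponential PFS and that patients stay on drug until progression or death. Sixteen weeks is 112 / 30.4375 = 3.68 months, so the fraction remaining is 0.5^(3.68/4.6) = 0.574, and 56 × 0.574 = 32.2.

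**5. Build-up over cycles.** Expected contributors out of 56. The first two columns use an exponential curve through the design rate, 56 × p^(t/16) with t in weeks. The third uses the 4.6-month median as in step 4.

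| Visit | Week | 20% at week 16 | 35% at week 16 | Median 4.6 months |
|---|---|---|---|---|
| C2D1 | 4 | 37.4 | 43.1 | 48.8 |
| C3D1 | 8 | 25.0 | 33.1 | 42.4 |
| C4D1 | 12 | 16.7 | 25.5 | 36.9 |
| C5D1 | 16 | 11.2 | 19.6 | 32.2 |

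Most patients still contribute at C2D1 in every column. By C5D1 between 24 and 45 of 56 do not.

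**6. Effect on the score.** If the missing patients had scores, the on-treatment mean would exceed the all-patient mean by (share missing) × (mean of those on drug − mean of those off drug). The documents give nothing for the second factor, and patients who have died have no score. The tendency can be argued, but its size in points cannot be derived.

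**The case against.** The best case for the plan is that describing quality of life during treatment is a coherent, if narrower, aim. This is a single-arm trial with no quality-of-life hypothesis, the instrument sits under correlative studies, and the 17-of-56 decision rule is untouched. All of that stands, and it limits the weight of the point. It does not answer the mismatch, because section 2.2 sets the objective for the treated population.

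Several stronger readings are tempting, and the documents do not support them:

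- *The data will describe only patients who are doing well.* Baseline, C1D15 and C2D1 forms come from most patients, including many who later fail. The first scheduled response evaluation is at 8 weeks (section 12.1).
- *Every last form predates the failure.* Forms come every 4 weeks and scans every 8, visits have a ±7-day window, and section 6.0 manages toxicity by interruption, reduction and 10 to 14 days of monitoring. Some Day 1 forms will fall during the toxicity or decline that ends treatment. What is usually missed is the state at discontinuation.
- *Only 11 to 20 patients will remain at C5D1.* Clinical benefit is a response endpoint and does not measure treatment persistence. The 4.6-month median gives about 32, though in a different population.
- *By-cycle means will look stable or improving, by a calculable number of points.* Section 15.2 specifies no such means, and any figure in points would need an assumed score difference and a mean that is undefined for the dead.
- *An EOT form cures the problem.* A patient who stops at week 8 still has no week-16 value, so a C5D1 mean rests on the same patients as before.

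**Conclusion.** The point holds as a cheap improvement to a secondary objective. All three schedule sections omit FACT-G7 at an EOT visit that already takes place, and treatment stops largely for reasons related to quality of life. Post-baseline data therefore come only from patients on drug, increasingly selected with each cycle, and later-cycle summaries will tend to be favourable relative to the stated objective.

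The illustrative extent at C5D1 is about 11 to 20 of 56 contributing at the design rates, if no benefit means off drug, or up to about 32 under an exponential PFS with the cited 4.6-month median. These figures count forms; they do not measure bias in the score. The primary endpoint, sample size, alpha and power are not affected.

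**What to change.** **Collection.** Add FACT-G7 to the EOT column and footnote 8 of the calendar, to section 9.1, and to the QOL Form row in section 11.0.

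**Analysis.** Add a short paragraph to section 15.2 that:

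- analyses change from baseline with the EOT value placed at its actual time since start of treatment, since EOT is not a fixed visit;
- reports form completion by cycle alongside any by-cycle means;
- labels those means as describing patients on treatment only.

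**Cost.** Seven items at an existing visit and one paragraph of text, with a slight added burden for patients. Some EOT forms will be missed, and selection from deaths and missed visits will be reduced but not removed. Patients already off treatment when the change is made cannot supply the form, but those still on drug can, and the section 15.2 text is useful in either case.
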